## **6.2 Dosage, Preparation and Administration of Study Products**

### **6.2.1 Dose and Regimen**

As outlined in [Section 4.2](#), each subject will receive injections with MRG-201 and placebo around the site of two separate 6-mm punch biopsies. The treatment for each wound site will be

randomized (left versus right) and blinded but consistent throughout dosing. MRG-201 and placebo will each be administered as four 20- $\mu$ L injections around one wound site, with subjects receiving approximately 5.3 mg of MRG-201 active moiety on each dosing day (approximately 1.3 mg per 20- $\mu$ L injection).

Study treatment injections for subjects receiving 6 doses in their initial treatment cycle will be administered on Days 1, 3, 5, 8, 10, and 12 of the first cycle of study dosing. A second cycle of 6 study treatment injections will be administered for subjects who exhibit evidence of keloid formation (defined as meeting a score of 1 or 2 on the mVSS and having an appearance consistent with an area likely to form a keloid according to investigator judgement) within 12 weeks after initiation of the first cycle of study dosing and following the initial 29-day treatment and assessment period. The treatment regimen for the second cycle of study dosing will be the same as for the first cycle, i.e., an initial dose on Day 1 followed by additional doses on Days 3, 5, 8, 10, and 12, with follow-up visits at Days 19 and 29 after the re-start of dosing.

Subjects in additional optional cohorts may receive blinded study treatment injections on Days 1, 3, 5, 8, 10, 12, 15, 17, 19, 22, 24, and 26 and will not be given a second cycle of dosing.

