### **7.2.2.1 *Pregnancy Test***

Female subjects must have a negative serum pregnancy test at screening and negative urine pregnancy tests at the subsequent time points specified in [Appendix A](#) and [Appendix B](#). A positive pregnancy test will result in immediate discontinuation of study treatment; however, study assessments will continue to evaluate study endpoints. All pregnancies will be followed through to outcome.

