### **8.3 Second Cycle of Dosing with MRG-201 and/or Placebo**

For subjects receiving 6 doses of MRG-201 in the initial treatment cycle, if there is evidence that a keloid may be forming (defined as meeting a score of 1 or 2 on the mVSS and having an appearance consistent with an area likely to form a keloid according to investigator judgement) within 12 weeks after initiation of the first cycle of study dosing, and following the initial 29-day treatment and assessment period, subjects will undergo a second cycle of study dosing in one or both biopsy sites (depending on keloid formation). Subjects will complete the procedures that were planned at the scheduled visit (e.g., Day 85 visit procedures, if that is the current visit), as well as be treated with MRG-201 or placebo according to the originally assigned study treatments. The study assessments to be performed during the second cycle of study dosing are summarized in [Appendix B](#).

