### **8.3.4 Day 8**

- Obtain vital signs (blood pressure, heart rate, respiratory rate, and body temperature).
- Perform a brief, symptom-directed physical examination.
- Collect blood (predose) for the following:
  - Hematology;
  - Clinical chemistry.
- Collect urine (predose) for urinalysis.
- Perform physician assessment of keloid formation and volume (predose).
- Assign mVSS and POSAS scoring ([Fearmonti et al 2010](#), see [Appendix D](#) and [Appendix E](#)).

- Administer intradermal study treatment(s).
- Review and record AEs and concomitant medications.

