#### **8.4.5 Days 15 and 22**

- Obtain vital signs (blood pressure, heart rate, respiratory rate, and body temperature).
- Perform a brief, symptom-directed physical examination.

- Collect blood (predose) for the following:
  - Hematology;
  - Clinical chemistry;
  - Antibody analysis.
- Collect urine (predose) for urinalysis (Day 15 only).
- Perform physician assessment of keloid formation and volume.
- Assign mVSS and POSAS scoring ([Fearmonti et al 2010](#), see [Appendix D](#) and [Appendix E](#)).
- Administer intradermal study treatments.
- Review and record AEs and concomitant medications.
- Note: Biopsy wound sites are to be photographed at the time the investigator suspects a keloid may be forming, at the time of observation of an unconfirmed keloid, and at the time of keloid confirmation.

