Abbreviations: AE = adverse event; aPTT = activated partial thromboplastin time; ECG = electrocardiogram; eCRF = electronic case report form; FSH = follicle-stimulating hormone; HIV = human immunodeficiency virus; INR = international normalized ratio; PK = pharmacokinetic(s); PT = prothrombin time; SAE = serious adverse event

- a) Day 1 refers to the first dosing day for the first double-blind active treatment period.
- b) Complete physical examination at screening and Day 1; brief physical examination at all other time points.
- c) Only for women who are not surgically sterile as confirmation of menopause.
- d) Serum pregnancy test at screening and urine pregnancy tests on Days 1, 12, 29, 85 and at the end of the study for female subjects.
- e) Performed at screening, predose on Day 1, on Day 2 (approximately 24 hours after Day 1 dosing), and predose on Day 12.
- f) Hematology, clinical chemistry, and urinalysis (including microscopy) will be collected predose as indicated in the protocol. Laboratory assessments do not need to be performed on Day 1 if screening laboratory measurements were performed within 3 days prior to Day 1.
- g) 6-mm punch biopsy to create two excisional wounds (one treated with MRG-201 and one treated with placebo on Day 1) as described in the Study Manual.
- h) Subjects will receive intradermal injections of MRG-201 and intradermal injections of placebo at each time point. Refer to the Study Manual for detailed instructions on intradermal injections – Biopsy Site Selection, Injection, and Brief Photography Instructions.
- i) All AEs, including SAEs, will be recorded from the time of administration of the first dose of study treatment on Day 1 until 30 days after the last dose of study treatment or the end of study visit, whichever occurs last. Treatment-related AEs ongoing at the follow-up visit should be followed to resolution or until the investigator considers them “chronic” or “stable.”
- j) All medications (including over-the-counter medicines, herbal treatments, supplements, and vitamins) administered 30 days before the first administration of study treatment (Day 1) until the end of study (Day 365) will be recorded on the eCRF.
- k) On Day 1 and Day 12, plasma for PK will be drawn at 1 hour ( $\pm$  10 minutes), 2 hours ( $\pm$  15 minutes), and 3 hours ( $\pm$  15 minutes) after injection.
- l) On Day 2 and Day 13, plasma for PK will be drawn 24 ( $\pm$  4) hours after Day 1/12 dosing.

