- c) Urine pregnancy test on Days 1 and 29 and at the end of the study for female subjects.
- d) Performed on Day 1 predose, on Day 2 (approximately 24 hours after Day 1 dosing), and predose on Day 12.
- e) Hematology, clinical chemistry, and urinalysis (including microscopy) will be collected predose as indicated in the protocol.
- f) Subjects will receive intradermal injections of MRG-201 and/or placebo at each time point, depending on the location of the suspected keloid. Refer to the Study Manual for detailed instructions on intradermal injections – Biopsy Site Selection, Injection, and Brief Photography Instructions.
- g) Physician Assessments will be completed predose on dosing visit days.

- h) All AEs, including SAEs, will be recorded from the time of administration of the first dose of study treatment on Day 1 until 30 days after the last dose of study treatment or the end of study visit, whichever occurs last. Treatment-related AEs ongoing at the follow-up visit should be followed to resolution or until the investigator considers them “chronic” or “stable.”
- i) All medications (including over-the-counter medicines, herbal treatments, supplements, and vitamins) administered 30 days before the first administration of study treatment (Day 1) until the end of study (Day 365) will be recorded on the eCRF.
- j) Photography of biopsy sites will be performed predose on Day 1. Refer to the Study Manual for detailed instructions.
- k) Following the visit that occurs 29 days after the start of the second cycle of study dosing, re-treated biopsy sites will be followed according to the first cycle visit schedule ([Appendix A](#)).
- l) End-of-study assessments will be performed on Day 365 or at the final visit for subjects who discontinue treatment early (if the subject has not withdrawn consent).

**Appendix C. Schedule of Events for Single Cycle of Dosing with MRG-201 and/or Placebo (12 Doses for Initial Treatment Cycle)**

Study Procedure	Screening (up to 28-day window)	Day 1 a	Day 2	Days 3, 5, 10, 12, 17, 19, and 24	Day 8	Days 15 and 22	Day 26	Day 27	Day 29 (±1 day)	Day 36 (±2 days)	Days 57, 113, 141, 197, 225, 281, 309, 337 (±7 days)	Day 85 (±7 days)	Days 169 and 253 (±7 days)	Day 365/ End of Study (± 7 days) o
Informed Consent	X													
Medical History	X													
Inclusion/Exclusion Criteria	X	X												
Vital Signs	X	X	X	X	X	X	X	X	X	X	X	X	X	X
Physical Examination b	X	X			X	X			X			X	X	X

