Weight	X								X			X		X
HIV, Hepatitis B, Hepatitis C	X													
FSH c	X													
Pregnancy Test d	X	X							X			X		X
12-lead ECG e	X	X	X						X					
Laboratory Assessments f	X	X	X		X	X			X			X	X	X
Serum Collection for Antibody Analysis		X				X (Day 15 only)			X			X	X (Day 169 only)	
6-mm Punch Biopsies g		X												
Study Treatment Injection h		X		X	X	X	X							
Physician Assessments for Keloid Formation and Volume					X	X			X		X	X	X	X
Modified Vancouver Scar Scale and POSAS					X	X			X		X	X	X	X
DLQI		X			X								X (Day 169 only)	X
Adverse Events i		X	X	X	X	X	X	X	X	X	X	X	X	X
Prior and Concomitant Medications j	X	X	X	X	X	X	X	X	X	X	X	X	X	X
PK Sample Collection		X k	X l				X k	X l						
Urine Sample Collection for PK m		X	X				X	X						

Photography of Biopsy Sites n		X						X			X	X	X
--	--	---	--	--	--	--	--	---	--	--	---	---	---

Abbreviations: AE = adverse event; aPTT = activated partial thromboplastin time; ECG = electrocardiogram; eCRF = electronic case report form; FSH = follicle-stimulating hormone; HIV = human immunodeficiency virus; INR = international normalized ratio; PK = pharmacokinetic(s); PT = prothrombin time; SAE = serious adverse event

- a) Day 1 refers to the first dosing day for the first double-blind active treatment period.
- b) Complete physical examination at screening and Day 1; brief physical examination at all other time points.
- c) Only for women who are not surgically sterile as confirmation of menopause.
- d) Serum pregnancy test at screening and urine pregnancy tests on Days 1 29, 85 and at the end of the study for female subjects.
- e) Performed at screening, predose on Day 1, on Day 2 (approximately 24 hours after Day 1 dosing), and predose on Day 29.
- f) Hematology, clinical chemistry, and urinalysis (including microscopy) will be collected predose as indicated in the protocol. Laboratory assessments do not need to be performed on Day 1 if screening laboratory measurements were performed within 3 days prior to Day 1.
- g) 6-mm punch biopsy to create two excisional wounds (one treated with MRG-201 and one treated with placebo on Day 1) as described in the Study Manual.

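### The 12-dose schedule and the second cycle have no scheduled pregnancy test between the Day 1 predose test and the last dose, so no scheduled test during dosing can trigger the pregnancy stop rule

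*Combined protocol and SAP*

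**What the plan says.** Section 7.2.2.1 sets the rule: "A positive pregnancy test will result in immediate discontinuation of study treatment". The test days are set separately for each dosing course.

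- **First 6-dose cycle** (Section 8.2, Appendix A footnote d): "urine pregnancy tests on Days 1, 12, 29, 85 and at the end of the study for female subjects". Section 8.2.6 makes the Day 12 test predose, so it precedes the sixth and last dose.
- **12-dose schedule** (Section 8.4, Appendix C footnote d): "Serum pregnancy test at screening and urine pregnancy tests on Days 1 29, 85 and at the end of the study for female subjects". Section 6.2.1 gives the dosing days as "injections on Days 1, 3, 5, 8, 10, 12, 15, 17, 19, 22, 24, and 26".
- **Second cycle** (Section 8.3, Appendix B footnote c): "Urine pregnancy test on Days 1 and 29 and at the end of the study for female subjects". Doses fall on cycle Days 1, 3, 5, 8, 10 and 12.

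The Day 1 test is predose in all three courses. Sections 5.3.1 and 9.7 also end dosing when a pregnancy becomes known, however it is found.

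**The concern.** A scheduled test can act on the stop rule during dosing only if it falls before the last dose. One of the three courses has such a test. The longest continuous course, 26 days, has none, and neither does the re-treatment cycle. The protocol gives no reason for the difference.

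It may be a by-product of adapting the 6-dose schedule. In the first cycle, weight, ECG and pregnancy test all sit on the last dosing day. In Appendix C all three sit on Day 29, although Sections 7.1.3 and 7.2.3 still place weight and a predose ECG on Day 26. That is inference; the documents do not say so.

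The matter is participant safety. It touches no endpoint or analysis. Section 2.1.3.2 records that Phase 1 enrolled only men, so the documents describe no earlier exposure of women. The case at issue is a pregnancy too early to detect on Day 1: dosing would run to completion before the next scheduled test.

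**Working it through.** No figure in the plan is at issue, so the check compares dosing days with test days. Dosing days come from Section 6.2.1. Test days and visit windows come from Sections 8.2 to 8.4 and Appendices A to C.

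| Course | Last dose | First scheduled test after Day 1 (earliest by window) | Tests after Day 1 predose and before last dose |
|---|---|---|---|
| First 6-dose cycle | Day 12 | Day 12, predose | 1 |
| 12-dose schedule | Day 26 | Day 29 ± 1 (Day 28) | 0 |
| Second cycle | Cycle Day 12 | Cycle Day 29 ± 3 (cycle Day 26) | 0 |

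The visit windows do not close the gap. The earliest next test is 28 − 26 = 2 days after the last dose in the 12-dose schedule, and 26 − 12 = 14 days after it in the second cycle.

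**Could a first-cycle test fall inside second-cycle dosing?** Section 8.3 ties the start of re-treatment to a scheduled visit, and the last dose comes 11 days after the start.

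- Start at the Day 29 visit (Days 26 to 32): last dose no later than Day 32 + 11 = 43.
- Start at the Day 57 visit (Days 50 to 64): last dose no later than Day 64 + 11 = 75. The Day 85 window opens on 85 − 7 = Day 78.
- Start at the Day 85 visit: the Day 85 test is the cycle Day 1 test.

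So there is no overlap. A start well after the Day 57 visit could bring the Day 85 visit into dosing, but Section 8.3.9 returns subjects to the first-cycle schedule only after cycle Day 29.

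**Doses after Day 1 with no further scheduled test, at 5.3 mg per dose**

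- 12-dose: 12 − 1 = 11 doses; 11 × 5.3 = 58.3 mg.
- Second cycle: 6 − 1 = 5 doses; 5 × 5.3 = 26.5 mg.

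**Interval between tests.** 29 − 1 = 28 days nominal: 27 to 29 in the 12-dose schedule and 25 to 31 in the second cycle.

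**Doses a predose test could spare, at most**

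- Day 15 of the 12-dose schedule (doses on Days 15, 17, 19, 22, 24, 26): 6 of 12; 6 × 5.3 = 31.8 mg.
- Day 8 of the second cycle (doses on Days 8, 10, 12): 3 of 6; 3 × 5.3 = 15.9 mg.
- Day 12 of either 6-dose cycle: 1 of 6; 5.3 mg.

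**The case against.** The strongest reply is that nothing in the protocol requires a test between doses. The tables, footnotes and visit text agree on the test days, so this is a design choice and not a contradiction. That is correct.

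The size can also be challenged. The counts of 11 and 5 are doses given without a further scheduled test, not doses that a test would have prevented. The protocol's own benchmark, the Day 12 test, spares one dose of six. The larger savings depend on the test days proposed here and on the test being positive by then. This stands, and the savings must be read as upper limits.

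Several safeguards lower the risk:

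- Women of child-bearing potential must use two contraceptive methods, one of them a barrier (Section 5.1).
- Women who reach a second cycle have already been tested at screening and during the first cycle.
- Subjects attend for every dose, with adverse event review each time.
- Section 2.1.3.1 reports nonclinical intradermal bioavailability of no more than 20%, half-lives mostly below 5 hours, similarly low systemic exposure in volunteers, and range-finding embryo-fetal studies with no relevant fetal exposure or external malformations.
- The 12-dose cohorts are optional, and a second cycle gives MRG-201 only if the MRG-201 site is re-treated.

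These points lower the consequence, but they leave the stop rule without a scheduled trigger during dosing in two of three courses.

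Day 8 of the second cycle is also only 7 days after the Day 1 test, so it can miss a very early pregnancy. That is a real weakness of the second-cycle remedy. The case for Day 15 is stronger.

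**Conclusion.** The concern holds. In the 12-dose schedule and the second cycle, no scheduled test after Day 1 can stop a dose. The change is worth making on safety grounds because it is cheap, though the risk is modest.

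The dose counts follow directly from the schedule. The milligram figures are injected amounts at the maximum 5.3 mg per dose, would be smaller in a lower-dose cohort, and do not measure systemic or fetal exposure. For the second cycle they apply only when the MRG-201 site is re-treated. The doses spared are upper limits because the documents do not say how soon a urine test turns positive. The documents give neither the number of women nor a pregnancy rate, so no expected number of exposed pregnancies can be derived.

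**What to change.** Add a urine pregnancy test for female subjects to the predose urine already collected on Day 15 of the 12-dose schedule (Section 8.4.5) and on Day 8 of the second cycle (Section 8.3.4). Amend those two sections, the pregnancy-test rows of Appendices B and C, Appendix B footnote c and Appendix C footnote d to match. In the same amendment, correct an editorial slip: Section 7.2.2.1 refers to Appendices A and B for the test days but omits Appendix C.

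The cost is one test strip per woman per cycle, plus a written amendment with sponsor approval and IRB review (Sections 12.4 and 14.2). No visit or sample is added. In the second cycle there is a trade-off. Testing on Day 12 would be less likely to miss an early pregnancy, but it could spare only 1 of 6 doses and would need a urine collection that Section 8.3.6 does not list.

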**Appendix D. Modified Vancouver Scar Scale**

	Scar Characteristic	Score
Vascularity	Normal	0
	Pink	1
	Red	2
	Purple	3
Pliability	Normal	0
	Supple	1
	Yielding	2
	Firm	3
	Ropes	4
	Contracture	5
Height	Flat	0
	<2 mm	1
	2-5 mm	2
	>5 mm	3
Total score		11

Derived from: [Fearmonti R, Bond J, Erdmann D, Levinson H. \(2010\) A review of scar scales and scar measuring devices. Eplasty 10:e43.](#)

## Appendix E. The Patient and Observer Scar Assessment Scale (POSAS) v 2.0 EN

## POSAS Observer scale

The Patient and Observer Scar Assessment Scale v2.0 / EN

Date of examination:

Name of patient:

### Observer:

10 of 10

[figure not shown]
[figure not shown]
---

**Location:**

Date of birth:

---

**Research / studies:**

### Explanation

The observer scale of the POSAS consists of six items (vascularity, pigmentation, thickness, relief, pliability and surface area). All items are scored on a scale ranging from 'like normal skin' to 'as far from normal as imaginable'.

to 10 ('worst scar imaginable'). The sum of the six items results in a total score of the POSAS observer scale. Categories boxes are added for each item. Furthermore, an overall opinion is scored on a scale ranging from 1 to 10. All parameters should preferably be compared to normal skin on a comparable anatomical location.

#### **Explanatory notes on the items:**

- **VASCULARITY** Presence of vessels in scar tissue assessed by the amount of redness, tested by the amount of blood return after blanching with a piece of Plexiglas
- **PIGMENTATION** Brownish coloration of the scar by pigment (melanin); apply Plexiglas to the skin with moderate pressure to eliminate the effect of vascularity
- **THICKNESS** Average distance between the subcutaneous-dermal border and the epidermal surface of the scar
- **RELIEF** The extent to which surface irregularities are present (preferentially compared with adjacent normal skin)
- **PLIABILITY** Suppleness of the scar tested by wrinkling the scar between the thumb and index finger
- **SURFACE AREA** Surface area of the scar in relation to the original wound area

## POSAS Patient scale

The Patient and Observer Scar Assessment Scale v2.0 / EN

Date of examination:

Name of patient:

[figure not shown]
Observer:

Date of birth:

Location:

Identification number:

Research / study:

1 = no, not at all

yes, very much = 10

HAS THE SCAR BEEN PAINFUL THE PAST FEW WEEKS?

1 = no, as normal skin

yes, very different = 10

HAS THE SCAR BEEN ITCHING THE PAST FEW WEEKS?

1

2

3

4

5

6

7

8

9

10

1

2

3

4

5

6

7

8

9

10

IS THE SCAR COLOR DIFFERENT FROM THE COLOR OF YOUR NORMAL SKIN AT PRESENT?

1

2

3

4

5

6

7

8

9

10

IS THE STIFFNESS OF THE SCAR DIFFERENT FROM YOUR NORMAL SKIN AT PRESENT?

1

2

3

4

5

6

7

8

9

10

IS THE THICKNESS OF THE SCAR DIFFERENT FROM YOUR NORMAL SKIN AT PRESENT?

1

2

3

4

5

6

7

8

9

10

IS THE SCAR MORE IRREGULAR THAN YOUR NORMAL SKIN AT PRESENT?

1

2

3

4

5

6

7

8

9

10

1 = as normal skin

very different = 10

WHAT IS YOUR OVERALL OPINION OF THE SCAR COMPARED TO NORMAL SKIN?

1 = as normal skin

very different = 10

## Appendix F. The Dermatology Life Quality Index (DLQI)

### DERMATOLOGY LIFE QUALITY INDEX (DLQI)

Hospital No: ..... Date: .....

Name: ..... Score: .....

Address: ..... Diagnosis: .....

The aim of this questionnaire is to measure how much your skin problem has affected your life  
OVER THE LAST WEEK. Please tick (✓) one box for each question.

1. Over the last week, how itchy, sore, painful or stinging has your skin been?	Very much 	A lot 	A little 	Not at all 
2. Over the last week, how embarrassed or self conscious have you been because of your skin?	Very much 	A lot 	A little 	Not at all 
3. Over the last week, how much has your skin interfered with you going shopping or looking after your home or garden?	Very much 	A lot 	A little 	Not at all  Not relevant 
4. Over the last week, how much has your skin influenced the clothes you wear?	Very much 	A lot 	A little 	Not at all  Not relevant 
5. Over the last week, how much has your skin affected any social or leisure activities?	Very much 	A lot 	A little 	Not at all  Not relevant 
6. Over the last week, how much has your skin made it difficult for you to do any sport?	Very much 	A lot 	A little 	Not at all  Not relevant 
7. Over the last week, has your skin prevented you from working or studying?	Yes 	No  Not relevant 		
If "No", over the last week how much has your skin been a problem at work or studying?	A lot 	A little 	Not at all 	
8. Over the last week, how much has your skin created problems with your partner or any of your close friends or relatives?	Very much 	A lot 	A little 	Not at all  Not relevant 
9. Over the last week, how much has your skin caused any sexual difficulties?	Very much 	A lot 	A little 	Not at all  Not relevant 
10. Over the last week, how much of a problem has the treatment for your skin been, for example by making your home messy, or by taking up time?	Very much 	A lot 	A little 	Not at all  Not relevant 

Please check you have answered EVERY question. Thank you.

